Patients enrolled in the non-SI screw removal treatment group will not undergo screw removal surgery. If complications arise and/or surgery is required, crossover will be allowed and recorded within study follow-up forms.

CLINICAL EVALUATION

A summary of the clinical evaluations is outlined below and can also be found in Appendix B.

Medical Record Review

At time of consent, information about the participant (medical history, height and weight, etc.) and the participant's injuries and hospital stay will be collected, including mechanism of injury, date and time of injury, presence of and severity of other orthopaedic and non-orthopaedic injuries, procedures done in the hospital, and SI screw surgery characteristics.

Assessment of Study Injuries

The following information will be obtained via medical record review and surgeon recall at the time of enrollment:

- Type of pelvic fracture
- Side of pelvic fracture
- SI joint displacement at time of SI screw stabilization surgery

Assessment of SI Screw Stabilization Surgery

The following information will be obtained via medical record review and surgeon recall at the time of enrollment:

- Type of fracture reduction
- SI screw placement characteristics

- Type of fracture fixation (if applicable)
- Acetabular fracture characteristics (if applicable)

Assessments at 6 months, 9 months, 12 months, 18 months, and 24 months Post SI Screw Stabilization Surgery

- Complications since last follow-up (type, severity, treatment)
- Assessment of fracture healing
- Weight bearing status and ambulation
- Use of ambulatory devices
- Pain assessment
- Narcotic use assessment

X-rays

AP and lateral x-rays at admission, post SI screw stabilization surgery, and at the 6 month, 9 month, 12 month, 18 month, and 24 month follow-ups will be obtained. These x-rays are obtained per standard of care.

PARTICIPANT INTERVIEWS

A summary of the participant interviews performed are outlined below and can also be found in Appendix D.

Enrollment Interview

At the time enrollment, participants will be asked about the following:

- Age, gender, race and ethnicity, and education
- Smoking history
- Previous injuries (specifically pelvis or back)
- Pain medication usage prior to pelvis injury
- Work and health status prior to pelvis injury
- General and pelvic function prior to pelvis injury

Follow-up Interviews

At 6 months, 9 months, 12 months, 18 months, and 24 months post SI screw stabilization surgery, participants will be asked about the following:

- Any re-hospitalization or outpatient surgery since the last visit for any reason related to his/her pelvic injury
- Rehabilitation received
- Pain medication usage
- Work Status Work Productivity and Activity Impairment
- Pain Brief Pain Inventory
- Health Status VR-12
- Pelvic Function Majeed Pelvic Score

STUDY SCHEDULE

Screening and Consent

All patients between the ages of 18 and 80 (inclusive) with pelvic fracture that required SI screw stabilization surgery will be screened for eligibility by the research coordinator or research team members in close coordination with the surgeon investigators. Screening will typically occur at the time of SI screw stabilization surgery and patients will be tracked until valid enrollment period opens (2 to 8 months post SI screw SI Screws - Protocol v4 (2022.08.19) Page 11 of 24

stabilization surgery). An eligibility checklist form will be completed on every potentially eligible participant and entered onto the electronic data capture system. The treating surgeon will be available via pager to answer questions regarding study eligibility. When the treating surgeon is not available, the study PI will be available to page. Contact information for the PI and alternate contact is available in Appendix A. In most cases, questions should be resolved at this level.

Once eligibility has been confirmed, the informed consent process will be completed by the research coordinator or research team member and attending surgeon. Patients will be approached about potential participation in the study at a standard of care clinic follow-up appointment between 2 and 8 months post SI screw stabilization surgery following determination of eligibility.

Enrollment

Once consented into the study, baseline data regarding participant characteristics, injury characteristics, fracture classification and medical history/co-morbidities will be collected. Characteristics about the hospital course and treatment received will also be collected. A brief interview will be conducted with the participant. All data will be recorded on the paper Case Report Form (CRF) and entered into the electronic data capture system.

Follow-up

Participants will return for follow-up visits at 6 months, 9 months, 12 months, 18 months, and 24 months post SI screw stabilization surgery. Participants will undergo a clinical evaluation by the treating surgeon and be interviewed by the research coordinator or research team member. These visits tend to mirror clinic visits per standard of care, however there may be some circumstances where patients are unwilling to return to the clinic. In these situations the research coordinator or research team member may obtain as much visit data as possible by phone and/or medical record review to prevent loss of important study information. All data will be recorded on the paper Case Report Form (CRF) and entered into the electronic data capture system.

Retention

Every effort will be made to retain participants in the study. We will keep participants engaged through use of study updates during non-study clinic appointments, and reminder calls/letters for upcoming appointment visit window timeframes.

Visit Windows

Each visit will have an interval of time surrounding the ideal date for the visit during which the visit may be completed and the data included in the trial database. This interval is approximately 2 weeks before or after the ideal date for a visit. Study data will still to be collected even if the visit falls out of the ideal window of time.

ASSESSMENT OF SAFETY

The study will monitor all complications and report adverse events to ensure participant safety. All local IRB requirements for reporting adverse events will be met.

The safety monitor (SM) is responsible for providing medical guidance and overseeing participant safety for the study. The SM participates in determining the course of action necessary to meet safety goals and objectives. This is achieved through the review of complications related or possibly related to study treatment, Serious Adverse Event (SAE) reports; resolving safety issues; and interacting with the Principal and Sub-Investigators at each site.

Reportable New Information (RNI)

The following information must be reported to the IRB within FIVE (5) business days of the investigator becoming aware of the information (please note that a separate RNI must be completed and submitted for each problem/event/report):

- Information that indicates a new or increased risk. For example:
 - New information (e.g., an interim analysis, safety monitoring report, publication in the literature, sponsor report, or investigator finding) indicates an increase in the frequency or magnitude of a previously known risk, or uncovers a new risk
 - An investigator brochure, package insert, or device labeling is revised to indicate an increase in the frequency or magnitude of a previously known risk, or describe a new risk
 - Withdrawal, restriction, or modification of a marketed approval of a drug, device, or biologic used in the research protocol
 - Protocol violation that harmed subjects or others or that indicates subjects or others might be at increased risk of harm
 - Complaint of a subject that indicates subjects or others might be at increased risk of harm or at risk of a new harm
 - Any changes significantly affecting the conduct of the research
- Any harm experienced by a subject or other individual which in the opinion of the local investigator is unexpected and at least probably related to the Human Research procedures and suggests that the research places subjects or others at a greater risk of harm than was previously known or recognized
 - A harm is "unexpected" when its specificity or severity are inconsistent with risk information previously reviewed and approved by the IRB in terms of nature, severity, frequency, and characteristics of the study population
 - A harm is "at least probably related to the Human Research procedures" if in the opinion of the local investigator, the research procedures more likely than not caused the harm (greater than 50% probability)
- Non-compliance with the federal regulations governing human research or with the requirements or determinations of the IRB, or an allegation of such non-compliance
- Failure to follow the protocol due to the action or inaction of the investigator or research staff
- Breach of confidentiality
- Change to the protocol taken without prior IRB review to eliminate an apparent immediate hazard to a subject
- Incarceration of a subject in a study not approved by the IRB to involve prisoners
- Complaint of a subject that cannot be resolved by the research team
- Premature suspension or termination of the research by the sponsor or the investigator
- Unanticipated adverse device effect (any serious adverse effect on health or safety or any lifethreatening problem or death caused incidence in the investigational plan or application – including a supplementary plan or application – or any other unanticipated serious problem associated with a device that relates to the rights, safety, or welfare of subjects)
- Audit, inspection, or inquiry by a federal agency
- Written reports of study monitors

Serious Adverse Event (SAE)

Serious Adverse Events may be discovered during regularly scheduled visits or though unscheduled participant contacts between visits. SAEs will be managed according to the medical judgment of the treating physician and source documentation will be maintained (e.g. laboratory and/or radiology reports, clinical notes, discharge summaries). The following are the categories considered for a serious adverse event and must be reported to the IRB during the continuing review process:

• Serious, unexpected, not related

- Is unexpected, in terms of nature, severity, or frequency, given the research procedures that are described in the protocol and informed consent document and the characteristics of the participants eligible for the study
- e.g. Death not due to study participation
- Serious, expected, related
 - Is related or possibly related to treatment/procedures under study; possibly related means there is a reasonable possibility that the incident, experience, or outcome may have been caused by the study procedures or treatments
- Serious, expected, not related

Study patients who experience an SAE will be followed until resolution of the event and a final report will be submitted to the safety monitor and IRB. Please note that SAE's and RNI's may overlap and a single event may be classified under both conditions.

DATA ANALYSIS

We are interested in estimating the causal effect of removal versus non-removal of SI screws in pelvic fracture patients requiring the use of SI screws for stabilization. Our primary hypothesis is that the SI screw removal group will have lower VAS pain scores compared to the non-SI screw removal group during their outpatient follow-up period. For all our analyses, we will report estimates of the causal effects, standard errors, and confidence intervals. We will also report the results of tests of null hypothesis of no causal effect.

RANDOMIZATION

Eligible patients will be randomized in equal proportions to one of the two treatment groups: 1) SI screw removal, 2) non-SI screw removal. Allocation will be concealed using a centralized 24-hour computerized randomization system, www.randomize.net, that will allow Internet based allocation. The treatment allocation will be stratified on the following prognostic factors to ensure balance between the intervention groups: 1) patient SI joint displacement at the time of injury.

DATA MANAGEMENT

Data will be collected in real time by the study investigators, research coordinator, or research team members, directly on paper Administrative Forms (AFs) or Case Report Forms (CRFs) which will serve as source documents for the study. The study personnel will obtain the information necessary to complete the case report forms (CRFs) from several sources including but not limited to, the patient's medical record, clinical evaluations and patient interviews. These forms will NOT contain the patient's name, SSN, or hospital medical record number; they will be identified only by a unique patient-specific study number. All data requested on the AF or CRF must be completed. Source documents will be signed by the study team member that has reviewed the AF or CRF. An electronic data capture system, REDCap, will be used to store data electronically after paper AF and CRF collection. On the monthly basis, the research coordinator will make a visual check of the data and will query all missing data, implausible data, and inconsistencies.

The REDCap data entry screens will be similar to the paper AFs and CRFs. Data integrity will be enhanced by using the electronic data capture system through a variety of mechanisms for checking data at the time of entry including referential data rules, valid values, range checks, and consistency checks against data already stored in the database. Clinical site personnel will be able to view and modify data for participants recruited from their clinical site only. Each time data is submitted or modified, it will be validated by the research coordinator. SI Screws - Protocol v4 (2022.08.19) Page 14 of 24

All AFs and CRFs must be kept secure in locked cabinets or other enclosures that are accessible only to study personnel. All electronic data must be password-protected and accessible only to study personnel. Study personnel will be responsible for backing up all electronically submitted data. Hard copy documents containing subject data and patient identifiers (and contact information) will be stored in secure document containers (file cabinets, lockers, drawers, etc.) in accordance with standard document management practices. Paper forms and the files containing personally identifiable data at each site will be destroyed within 5 years of study completion.

Quality control quality assurance procedures will be in place for the duration of the study. Ongoing data edits and internal audits will be performed to ensure collection of quality data. The continuous and timely flow of data from the AFs and CRFs to the REDCap electronic data capture system is an essential prerequisite for maintaining data quality.

Monthly performance reports will be completed by the research coordinator summarizing among other things: recruitment, status of follow up, data completion, and timelines of data entry.

MISSING DATA

As with most prospective studies, missing data will be unavoidable, even with excellent follow up. Since the informative nature of missing data cannot be verified from the observed data, we will adopt a sensitivity analysis framework for reporting results. We will analyze data under a variety of modeling assumptions regarding how strongly the missingness mechanism is related to outcomes. Regarding study conduct, we will:

- 1. Limit participant burden and inconvenience in data collection
- 2. Select high quality research team members
- 3. Monitor and report missing data rates during the study
- 4. Emphasize the importance of full participation in the study during the consent process
- 5. Collect information on the reasons for missing data
- 6. Actively engage participants in the study and educate them about the importance of their engagement
- 7. Collect surrogate information on participants who miss clinic visits
- 8. Hold regular meetings to discuss strategies for enrollment and engagement of participation

While these efforts will help to minimize missing data, we recognize that missing data is inevitable.

RESEARCH ETHICS APPROVAL

This protocol, DSMB plan, consent forms, the AFs, and the CRFs have been reviewed and approved by University of Maryland Institutional Review Board (IRB).

INFORMED CONSENT

Both a Randomized Control Trial (RCT) consent and Observational (OBS) consent has been prepared for the study and is attached in Appendix C. The consent form describes the purpose of the study, the procedures to be followed, and the risks and benefits of participation. Copies of the signed consent forms will be given to the patient, and this fact will be documented in the patient's record.

Eligible patients will be approached for their consent to participate. Informed consent will be obtained prior to treatment group assignment.

To encourage a high level of participation from eligible patients, the attending surgeon will be involved in the consent conversation. The conversation will be initiated by the research coordinator or research team member and the surgeon together. Patients will be informed of the risks and benefits of participation and what will be expected of them if they choose to participate. Consent will be obtained in accordance with principles of GCP and ICH guidelines.

The study should be presented as a randomized control trial upon initial consent conversation. If the patient declines to participate after full understanding of the trial, only then should the observational arm be presented.

VULNERABLE POPULATIONS

The study will not include children, pregnant women, or prisoners.

PARTICIPANT CONFIDENTIALITY

It is the investigator's responsibility to conduct the protocol under the current version of Declaration of Helsinki, ICH Guidelines, Good Clinical Practice, and rules of local IRBs. The investigator must ensure that the patient's anonymity be maintained.

Participants will be identified only by an identification code but not by their name, SSN, or hospital medical record number. The research coordinator will maintain a separate confidential enrollment log which matches identifying codes with patient names and addresses available only to research staff.

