	approximately 150 (75 per arm) will be enrolled in the randomized arm					
	of the study with a 12 month follow-up for the primary outcome					
Diagnosis and Main	Pelvic fracture requiring SI screw placement in patients between the ages					
Inclusion Criteria	of 18 and 80 years of age, inclusive					
Length of Follow-up	24 months					

Study duration: We will recruit for two and a half years. Patients will be followed for 24 months. We estimate 6 years total.

Primary outcome measure: *Patient-reported pain* as measured by using the arithmetic mean of the four pain severity items on the patient-reported Brief Pain Inventory assessment (BPI) 12 months following the patient's injury.

Secondary outcome measures:. Pelvic function will be measured using the Majeed Pelvic Score.

Statistical analysis: We are interested in estimating the causal effect of removal versus non-removal of SI screws in pelvic fracture patients requiring the use of SI screws for stabilization. For all our analyses, we will report estimates of the causal effects, standard errors, and confidence intervals. We will also report the results of tests of null hypothesis of no causal effect.

KEY ROLES

Safety Monitor- [name] will be responsible for overseeing patient safety for the study. [name] will review the enrollment numbers, adverse events, and medical compliance annually for the duration of the study.

Principle & Sub-Investigators- [name] (PI) and the sub-investigators will be responsible for developing a detailed study protocol, providing oversight on study progress and act to correct deficiencies in the conduct of the study. The PI and sub-investigators will also draft the main publications related to the study, and assist with patient consent.

Research Coordinator- [name], research specialists, are responsible for maintaining all study documentation, developing and maintaining the master IRB application and consent, circulating any changes to study documents including protocols, case report forms, and IRB materials to the research team members, providing daily oversight and management of study implementation, performing data quality control and analysis of study results, and conducting monthly reports for the study.

Research Team Members- The research team members are responsible for the conduct of the clinical study including patient enrollment, performing study procedures, data collection and conducting study follow-up visits.

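### The 12-month pain score is taken in an interview by staff who will normally know the arm, and the coordinator role also analyses the results, so avoidable interviewer and analyst bias could enter.

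*Combined protocol and SAP*

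**What the plan says.** The Primary Endpoint section and the Protocol Summary make patient-reported pain severity on the BPI the primary outcome, scored as the mean of its four severity items and assessed at 12 months.

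**Collection.** Participant Interviews, under Follow-up Interviews, lists "Pain Brief Pain Inventory" among the topics at 6, 9, 12, 18 and 24 months. The same list asks about re-hospitalization or outpatient surgery related to the pelvic injury since the last visit. Study Schedule, under Follow-up, says participants are examined by the treating surgeon and are to "be interviewed by the research coordinator or research team member". Phone contact or record review is allowed for those unwilling to return to clinic.

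**Consent.** Study Schedule, under Screening and Consent, says "the informed consent process will be completed by the research coordinator or research team member and attending surgeon". Informed Consent adds: "The conversation will be initiated by the research coordinator or research team member and the surgeon together".

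**Data checks.** Data Management says that each month "the research coordinator will make a visual check of the data and will query all missing data, implausible data, and inconsistencies".

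**Analysis.** Key Roles gives the research coordinator, a role held by research specialists in the plural, responsibility for "performing data quality control and analysis of study results". Research team members are a separate role, with enrollment, procedures, data collection and follow-up visits as duties. Analysis is not among them.

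**Masking.** The supplied text does not mention masking of interviewers, data reviewers or analysts, and it names no independent assessor or statistician. Randomization provides for concealed allocation through a central web system.

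**The concern.** Pain severity is subjective, and the two arms cannot be made to look alike to the patient. That makes the avoidable sources of bias worth controlling. There are two here.

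- **The interviewer.** Someone who knows the arm can influence answers through tone, prompting or how a hesitant reply is recorded.
- **The analyst.** Someone who knows the arm can be influenced in choosing the model, covariates or analysis set. Data Analysis specifies none of these, and Missing Data allows a range of modelling assumptions.

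Primary Objective and Data Analysis both state a hypothesis in favour of removal. If either influence operated, the natural direction would be towards that hypothesis. A positive result would then be open to a criticism that could have been prevented at little cost. Concealed allocation does not answer it, because concealment protects the assignment and not what is measured or analysed afterwards.

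**Working it through.** **Step 1. Would the interviewer know the arm?** The protocol never says that staff are unmasked; this has to be inferred. Four features point the same way.

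- Study Treatments compares a removal operation with no operation, and no sham is described.
- The follow-up interview that contains the BPI also asks about pelvic surgery since the last visit.
- Clinical Evaluation schedules x-rays at every follow-up, and Appendix B has forms for treatment and crossover removal surgery.
- The interviewer may be the person who took consent.

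The order of questions is not fixed. Follow-up Interviews lists surgery first; Appendix B lists the BPI first; neither is stated to be the order of administration.

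**Step 2. Which duties can fall to one role?**

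| Duty | Who | Where |
|---|---|---|
| Consent | coordinator or team member, with surgeon | Screening and Consent; Informed Consent |
| BPI interview | coordinator or team member | Follow-up |
| Monthly check and queries | coordinator | Data Management |
| Analysis of results | coordinator | Key Roles |

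The coordinator role is therefore eligible for all four duties. Two are shared with team members and two are not. The overlap is permitted; it is not required.

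**Step 3. How large could it be?** The protocol has no figure to reproduce. It gives about 150 randomized (75 per arm, equal allocation) without an alpha, power, target difference, SD or dropout rate. The following is illustration only.

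Inputs: n = 75 per arm from the Protocol Summary. Assumed: two-sided alpha 0.05, BPI severity SD 2.0 to 2.5, complete follow-up, no true effect, and a shift b in the difference between arms caused by measurement.

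- SE = SD × √(2/75). At SD 2.25: 2.25 × 0.1633 = 0.367.
- Rejection rate = Φ(b/SE − 1.96) + Φ(−b/SE − 1.96).
- For b = 0.2 at SD 2.25: b/SE = 0.544, giving Φ(−1.416) + Φ(−2.504) = 0.078 + 0.006 = 0.085 before further rounding (8.5% to one decimal, just under that unrounded, so 8%).

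| Assumed SD | b = 0.2 | b = 0.3 | b = 0.5 |
|---|---|---|---|
| 2.0 | 9.4% | 15.1% | 33.4% |
| 2.25 | 8.5% | 12.9% | 27.5% |
| 2.5 | 7.8% | 11.4% | 23.2% |

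In whole percentages the middle row is 8%, 13% and 27% (the last is 27.499% before rounding). The table shows what a shift would do if it existed. It does not show that one exists, and it cannot separate interviewer influence from patient expectation. The analyst's contribution is not quantified.

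**The case against.** The strongest reply has four parts.

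**The BPI is a patient-reported questionnaire.** Primary Endpoint describes it that way, Potential Risks mentions stored paper questionnaires, and Appendix B puts it under patient rather than clinical follow-up. No section says that staff rate or interpret the pain items. This stands in part: self-completion may be what was intended. But Participant Interviews places the BPI in an interview, and Follow-up has staff conduct it, so the current text does not secure self-completion.

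**One person need not do everything.** This stands. The consent and interview text offers a team member as the alternative, and several people hold the coordinator role. A reader might infer that one individual consents, interviews, queries and analyses; the documents only fail to prevent it.

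**Two stronger readings go beyond the text.** A reader might infer that the mode of collection will differ by arm. Both arms have the same visit schedule, and phone contact depends on unwillingness to attend. Study Treatments schedules removal at 5 to 9 months, so the 12-month visit falls 3 to 7 months later (12 − 9 and 12 − 5). Nothing indicates different attendance by then. A reader might also infer that pain scores will be queried selectively. Data Management has the coordinator query all missing, implausible and inconsistent data, alongside range and consistency checks at entry. Nothing shows how an in-range pain rating would be challenged in one direction.

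**Patients know their arm anyway.** This is true, and no change to staffing removes their expectation. It does not justify adding interviewer and analyst influence that can be avoided.

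**Conclusion.** The point holds as a low-cost improvement. The primary pain score is collected in an interview by staff who will normally know the arm; the coordinator role may also take consent and is assigned the analysis; and the protocol neither masks nor separates these duties. Interviewer and analyst bias could enter. The documents do not show that it will.

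Its size is unknown. The 8%, 13% and 27% rejection rates rest on an assumed SD of 2.25, assumed shifts, an assumed two-sided 5% test and full follow-up of 75 per arm. They should not be used to grade the problem. The conclusion rests on the assignment of duties and the interview content, not on those figures.

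**What to change.** **Participant Interviews and Study Schedule (Follow-up).** State that the participant completes the BPI, on paper or through a REDCap survey, before any contact with the surgeon or coordinator at that visit and before the questions on surgery and re-hospitalization. Keep the phone fallback. When it is used, read the BPI items verbatim and ask them first. Record the mode of completion for every visit.

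**Key Roles and Data Analysis.** State that the primary analysis is run on coded arm labels, with the model fixed before the code is opened, where possible by an existing team member who did not interview participants. Coded labels achieve little unless the model is written down first, so the two belong together.

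**Cost.** Protocol wording and a survey form in a system already in use. The protocol gives no staff numbers, so the separate analyst is put as a preference and not a requirement. Self-completed forms will need reminders. Some phone participants may reveal their arm, and a coordinator who took consent may already know it; verbatim reading limits prompting but does not mask. Treatment, eligibility and the visit schedule are unchanged.
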